#### 9.4.4 Procedures for Handling Missing Serum Phosphorus Data

Descriptive summaries of efficacy and safety measures will be based on observed data. No imputation of missing data will be implemented.

Handling of missing data for each inferential analysis will be detailed in the SAP.

# 9.4.5 Methods of Pooling Data

For the purpose of adjusting for investigator effects in statistical models, investigator sites may be pooled into groups based on geographic region and number of patients enrolled with an aim for comparable sample sizes among pooled investigator sites. The goal of the pooling strategy will be to avoid less than a minimum number of patients per pooled investigator site. The size of a pooled investigator site would generally depend on the enrollment size for each individual investigator site. The pooled investigator sites will be used in all applicable analyses where adjustment for investigator effect is desired.

Protocol No.: TEN-02-401

Edition No.: 1

#### 9.4.6 Visit Windows

No analysis visit windows will be formally defined. The schedule of events in Section 1.3 details the intended collection of study variables at specified visits. Should additional data be collected between scheduled visits, these data will be included in the patient data listings but ignored for analyses purposes, unless the additional data are the last data collected during each study period.

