- h Guidelines will be provided to limit the amount of concomitant medication information collected.
- Investigators can adjust doses of tenapanor or sevelamer between visits via telephone. Sevelamer can be re-dispensed at Visits 2, 3, 4, 5, and 8 if dose permits.
- k Sevelamer can be re-dispensed, if enough drug is left until the next visit. Drug accountability is also performed.
- Body weight is for HD patients only, height from TEN-02-301, and Kt/V can be taken from most recent standard-of-care assessment.
- m Major medical conditions taken from TEN-02-301.

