The theoretical adverse effects from tenapanor treatment in ESRD patients would be due to exaggerated pharmacological effects and may include electrolyte disturbances, metabolic acidosis, soft stools/diarrhea and reduced blood pressure. While a softening/loosening of the stool with an increased fluid loss via the intestine is an intended and desired effect of tenapanor in some patients, sensitive patients should be monitored for signs of dehydration in case of prolonged severe diarrhea. This study protocol includes clinical laboratory tests (including bicarbonate and electrolytes) and vital signs as well as specific discontinuation criteria related to phosphorus control to mitigate risks to study participants as well as to reduce the risk for severe hyper- or hypophosphatemia during the study and limit the period with risk for suboptimal phosphorus control. All patients will re-start their pre-study treatment with phosphate binders when their participation in the study ends. ESRD-HD patients are dialyzed three times per week and their health status is checked at each visit as part of standard of care. See the Investigator's Brochure for details on non-clinical and clinical results with tenapanor.

Patients will be informed both verbally and in writing about these aspects before taking part in any study-specific examination and the study will be conducted under conditions that ensure a high probability for the early detection of untoward events and for appropriate intervention.

In summary, the risks to the participants in this up to 18 month study are considered acceptable and the study results will be important for the development of a potential new drug, which could improve the treatment of hyperphosphatemia in this patient group.

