#### **Tenapanor Arm**

The dosing regimens described below for sevelamer are for guidance to the Investigators. Investigators have flexibility to dose sevelamer, TID, BID or QD based on their experience with each patient or as per package insert. Dosing regimens can be adjusted based on the most recent sP laboratory data (central laboratory data or standard of care local laboratory data).

If patients are in the tenapanor arm (from the TEN-02-301 study), sevelamer will be added as described below:

- $sP \ge 2.5$  and  $\le 4.5$  mg/dL: no addition of sevelamer.
- sP > 4.5 and  $\leq 5.0$  mg/dL: add one 800 mg tablet QD.
- sP > 5.0 and  $\leq 5.5$  mg/dL: add one 800 mg tablet BID.
- sP > 5.5 mg/dL: add one 800 mg tablet TID.

If sP is still greater than or becomes >4.5 mg/dL at a subsequent visit, sevelamer dose can be increased in a stepwise manner as described below:

- sP >4.5 and  $\le$ 5.0 mg/dL: add one 800 mg tablet to the existing regimen.
- sP > 5.0 and  $\leq 5.5$  mg/dL: add two 800 mg tablets to the existing regimen.
- sP > 5.5 mg/dL: add three 800 mg tablets each day (800 mg TID) to the existing regimen.

The maximum dose of sevelamer should be based on standard of care, the sevelamer package insert, and the Investigator's experience with each patient.

If sP < 2.5 mg/dL at any visit

- Sevelamer dose can be lowered by one 800 mg tablet TID, or as appropriate, based on current regimen; Investigators have flexibility to dose sevelamer BID or QD based on their experience with each patient or as per package insert.
- If patient is not taking sevelamer then tenapanor dose can be lowered by one 10 mg tablet BID, unless already at tenapanor 10 mg BID, then can dose tenapanor 10 mg QD

Protocol No.: TEN-02-401

Edition No.: 1

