# 7.2.6 Analysis of Clinical Laboratory Tests

A certified laboratory will be used to process and provide results for the clinical laboratory tests.

For any laboratory test value outside the reference range that the Investigator considers clinically significant, the Investigator will:

- Repeat the test to verify the out-of-range value.
- Follow the out-of-range value to a satisfactory clinical resolution.
- Record as an AE any laboratory test value that (1) is confirmed and the Investigator considers clinically significant, or (2) that requires a patient to be discontinued from the study, or (3) that requires a patient to receive treatment, or (4) fulfills one or more SAE criteria.

Protocol No.: TEN-02-401

Edition No.: 1

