#### 8.6 Unscheduled Visits

Unscheduled visits, for missed scheduled visits or safety or tolerability related reasons are allowed. Procedures performed are at the discretion of the Investigator.

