### 9.4.7 Safety Analyses

Safety analyses include summaries for adverse events, clinical laboratory tests, vital signs, body weights, 12-lead ECGs, and physical examinations. These summaries will be provided for the Safety Analysis Set and each TEN-02-301 treatment arm (tenapanor or sevelamer).

Adverse events will be coded using the Medical Dictionary for Regulatory Activities (MedDRA). Summary tables and listings will be provided by system organ class and preferred term for treatment-emergent adverse events (TEAEs). Actual values and change from baseline values for clinical laboratory tests, vital signs, body weights, and ECGs will be descriptively summarized by visit. The number and percentage of patients in each physical examination category will be presented by visit.

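### Apart from the last data in a study period, between-visit laboratory, vital-sign and ECG values are listed only, so abnormal ones that do not become AEs reach no safety table

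*Combined protocol and SAP*

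**What the plan says.** Section 9.4.6 defines no analysis visit windows. For data that arise between scheduled visits it states that "these data will be included in the patient data listings but ignored for analyses purposes", and adds one exception: "unless the additional data are the last data collected during each study period". Neither part distinguishes efficacy from safety data.

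Other sections create between-visit values for safety reasons:
- Section 8.6: "Unscheduled visits, for missed scheduled visits or safety or tolerability related reasons are allowed".
- Section 7.2.6 tells the investigator, for an out-of-range result considered clinically significant, to "Repeat the test to verify the out-of-range value".
- Section 7.2.4 permits extra ECGs where there is a clinical reason.

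The planned numerical safety output is in section 9.4.7: "Actual values and change from baseline values for clinical laboratory tests, vital signs, body weights, and ECGs will be descriptively summarized by visit". Treatment-emergent AEs are tabulated separately by system organ class and preferred term. The protocol plans no worst-value table, no shift table and no count of patients who ever cross a threshold.

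**The concern.** Values taken off schedule are often taken because something looked wrong. Leaving them out of analysis therefore removes values selectively, and towards a cleaner picture.

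This matters here for two reasons. Comparing long-term safety is a secondary objective (section 3.2). And the study treats towards a serum phosphorus (sP) range of 2.5 to 4.5 mg/dL, so values below the range are foreseeable. Section 2.5 describes safeguards meant to "reduce the risk for severe hyper- or hypophosphatemia during the study", and the dosing guidance repeatedly uses sP <2.5 mg/dL as a trigger for action. Yet no planned table shows how many patients ever fell below that level.

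**Working it through.** The plan gives no figure to reproduce: no expected rate of low sP and no expected number of unscheduled tests. The check is mainly a comparison of sections.

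**1. What the by-visit tables can contain.** Scheduled post-baseline measurements per patient, from the Schedule of Events (section 1.3):
- sP: 6 (Weeks 1, 2, 3, 4, 6, 8) + 6 (Months 3, 6, 9, 12, 15, 18) = 12. None at the ten telephone visits.
- Clinical laboratory tests: 6, the first at Month 3.
- Vital signs: 6 by the schedule (section 7.2.3 says at all patient visits).
- ECG: 1, at Month 18.

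So an ECG done for a clinical reason before Month 18, or an electrolyte result prompted by symptoms in the first weeks, has no scheduled counterpart near it in time.

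**2. Where an abnormal between-visit value goes.**
- By-visit tables (9.4.7): excluded by 9.4.6 unless it is the last data of a study period.
- AE tables: included if it becomes an AE. Section 7.2.6 gives four alternative routes for a laboratory value: confirmed and considered clinically significant; requires discontinuation; requires treatment; meets a serious-AE criterion.
- Otherwise: listings only. A low sP that is handled by reducing study drug, and is not judged clinically significant, can end here.

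**3. What the exception does.** Study period is not defined. If the whole treatment phase is one period, take two patients with the same abnormal unscheduled value. One leaves without a further assessment: the value is the last data and is analysed. The other stays and attends the next visit: the value is ignored. Sections 5.3 and 8.7 ask for the end-of-treatment assessments at withdrawal, if possible, so the difference arises when these are not done. The text also does not say in which by-visit row such a last value would appear.

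**4. Direction and size.** Adding measurements cannot reduce the number of patients with at least one low value, so the direction needs no assumption. The size does. For illustration, let each sP be <2.5 mg/dL with constant probability p, independently. The share of patients with any low value among n measurements is 1 − (1 − p)^n, and the share of affected patients missed by the 12 scheduled values is 1 − [1 − (1 − p)^12] / [1 − (1 − p)^n]. Both p and the number of extra values are assumptions.

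| p | n = 12 | n = 15 (3 extra) | missed | n = 22 (10 extra) | missed |
|---|---|---|---|---|---|
| 0.5% | 5.8% | 7.2% | 19% | 10.4% | 44% |
| 1% | 11.4% | 14.0% | 19% | 19.8% | 43% |
| 2% | 21.5% | 26.1% | 18% | 35.9% | 40% |
| 5% | 46.0% | 53.7% | 14% | 67.7% | 32% |

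With no extra values nothing is missed. The result follows mainly the assumed number of extra tests, on which the documents are silent. A constant p also ignores dose changes after a low value. None of these percentages is an estimate for this trial.

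**The case against.** The case on the other side is substantial, and most of it limits the point without removing it.

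- *The data are not ignored in every analysis.* A reader might infer that they are. The exception for last data is in the same sentence, and the AE tables are not confined to scheduled visits. This stands.
- *Hypophosphatemia is not undercounted.* That is a tempting reading, but no count of patients with sP <2.5 mg/dL is planned, so no planned estimate is biased. The defect is that the table is absent and that 9.4.6, as worded, would keep unscheduled values out of one. This stands.
- *Local sP results are not shown to be discarded by 9.4.6.* Section 4.1.1 lets local standard-of-care sP guide dosing, and a footnote to section 1.3 says "Investigators can adjust doses of tenapanor or sevelamer between visits via telephone". But study sP is a central laboratory measurement, and nothing says that local results enter the database. An analysis rule cannot be faulted for dropping data not shown to be collected. The n = 22 column above would need monthly local testing and so does not measure the effect of 9.4.6.
- *Some extremes are already visible.* Section 9.4.1 includes minimum and maximum, and the two response rates in section 7.3 differ at each visit by roughly the share of patients at or below 2.5 mg/dL. True, but for scheduled values only, and per visit, not per patient.
- *A repeat test verifies a value already obtained.* If that value was scheduled, it stays in the table. The repeat rule matters chiefly when the initial value was itself unscheduled.
- *Section 9.1 defers to a separate SAP that governs.* No SAP text is in the document reviewed, and it may already contain such a table. That would answer the point, but section 9.4.6 should then be expressly overridden.
- *The study is open-label and largely descriptive, with no statistical basis for its 150 to 200 patients.* This limits the weight of the point. It does not justify omitting safety values from the description.

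**Conclusion.** The point holds in a limited form. As written, sections 9.4.6 and 9.4.7 together keep between-visit laboratory, vital-sign and ECG values out of the safety tables, unless they are the last data in an undefined study period or become AEs. Inclusion of an unscheduled value can depend on whether the patient remains in the study.

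The documents support the direction (fewer extremes shown) but no magnitude. They do not support a claim that all hypophosphatemia is missed, that a planned count is biased, or that any particular share of affected patients is lost. The conclusion assumes that the separate SAP does not already provide an any-time table. It is worth correcting because long-term safety is a stated objective and the change is small.

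**What to change.** 1. In section 9.4.6, limit the exclusion of between-visit data to by-visit summaries, and define study period.
2. In section 9.4.7, add a per-patient worst post-baseline table with shift from baseline, covering sP <2.5 mg/dL, key electrolytes such as potassium and sodium, bicarbonate, blood pressure and investigator-assessed ECG. Use all scheduled, repeat and unscheduled study values. Show the number of measurements per patient beside it.
3. Separately, as a data-capture matter and not a consequence of 9.4.6: local sP values that trigger a dose change could be recorded in the eCRF with date and a local flag, and the table shown with and without them.

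The cost is a wording change, one set of tables and, for item 3, one eCRF field. By-visit tables are unchanged, and no dosing or clinical rule is touched. The downside is that patients tested more often have more chances of an extreme value, which is why the measurement count is shown, and reported abnormality rates may rise somewhat.

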### 9.4.7 Safety Analyses

Safety analyses include summaries for adverse events, clinical laboratory tests, vital signs, body weights, 12-lead ECGs, and physical examinations. These summaries will be provided for the Safety Analysis Set and each TEN-02-301 treatment arm (tenapanor or sevelamer).

Adverse events will be coded using the Medical Dictionary for Regulatory Activities (MedDRA). Summary tables and listings will be provided by system organ class and preferred term for treatment-emergent adverse events (TEAEs). Actual values and change from baseline values for clinical laboratory tests, vital signs, body weights, and ECGs will be descriptively summarized by visit. The number and percentage of patients in each physical examination category will be presented by visit.

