eligible to enroll into TEN-02-401 (NORMALIZE).

Patients will be required to sign an ICF and meet all inclusion/exclusion criteria. No baseline assessments will be performed as part of this protocol; all baseline data for TEN-02-401 will be taken from the TEN-02-301 End of Treatment (EOT) visit. Patients from the TEN-02-301 tenapanor arm will either receive only tenapanor or be given sevelamer in addition to tenapanor based on their sP. Patients from the TEN-02-301 sevelamer arm will be given tenapanor in addition to their sevelamer dose and the sevelamer dose will then be adjusted based on their sP following a protocol-specified dose titration schedule. Patients will be monitored for safety and efficacy with inoffice and telephone visits for up to an additional 18 months.

All study visits must be scheduled after a short dialysis interval (only for HD patients; e.g., Wednesday or Friday for patients on a MWF schedule and Thursday or Saturday for patients on a TThS schedule). Body weight and blood collections for laboratory assessments must be performed pre-dialysis. All other assessments may be performed pre-during, or post-dialysis but should be performed at the same time at each visit. For patients receiving PD, visits should be performed on the same day each week, if possible.

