# **Safety Analyses:**

All safety measures will be descriptively summarized for the Safety Analysis Set and each TEN-02-301 treatment arm (tenapanor or sevelamer).

Adverse events will be coded using the Medical Dictionary for Regulatory Activities (MedDRA) and will be summarized by system organ class and preferred term.

Actual values and change from baseline values for clinical laboratory tests, vital signs, body weights, and ECGs will be descriptively summarized by visit. The number and percentage of patients in each physical examination category will be presented by visit.

Protocol No.: TEN-02-401

Edition No.: 1

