# 3.2 Secondary Objectives

The secondary objectives of this study are:

- To compare the phosphorus lowering effect of tenapanor and sevelamer alone in patients with sP >4.5 mg/dL to patients treated with a combination of tenapanor and sevelamer.
- To evaluate the effect of tenapanor alone and in combination with sevelamer on the proportion of patients reaching serum phosphorus targets defined as ≤4.5 mg/dL.
- To evaluate the effect of the addition of tenapanor to patients taking sevelamer on the percentage reduction in the sevelamer dose.
- To evaluate the effect of tenapanor alone and in combination with sevelamer on intact fibroblast growth factor 23 (iFGF23).
- To evaluate the effect of tenapanor alone and in combination with sevelamer on the Kidney Disease Quality of Life (KDQoL) survey.
- To evaluate the effect of tenapanor alone and in combination with sevelamer on the Dialysis Symptom Index (DSI) survey (for English speakers only).
- To compare the long-term safety of tenapanor alone and in combination with sevelamer.

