#### 4 STUDY DESIGN

# 4.1 Design Summary

Patients who complete the TEN-02-301 study (PHREEDOM) at Visit 23, may be eligible to enroll into TEN-02-401 (NORMALIZE).

Patients will be required to sign an ICF and meet all inclusion and no exclusion criteria. No baseline assessments will be performed as part of this protocol; all baseline data for TEN-02-401 will be taken from the TEN-02-301 End of Treatment (EOT) visit. Patients from the

Protocol No.: TEN-02-401

Edition No.: 1

TEN-02-301 tenapanor arm will either receive only tenapanor or be given sevelamer in addition to tenapanor based on their sP following a protocol-specified dose titration schedule. Patients from the TEN-02-301 sevelamer arm will be given tenapanor in addition to their sevelamer dose and the sevelamer dose will then be adjusted based on their sP following a protocol-specified dose titration schedule. Patients will be monitored for safety and efficacy with in-office and telephone visits for up to an additional 18 months.

All study visits must be scheduled after a short dialysis interval (only for HD patients; e.g., Wednesday or Friday for patients on a MWF schedule and Thursday or Saturday for patients on a TThS schedule). Body weight and blood collections for laboratory assessments **must** be performed pre-dialysis. All other assessments may be performed pre-, during, or post-dialysis but should be performed at the same time at each visit. For patients receiving PD, visits should be performed on the same day each week, if possible.

Investigators may decrease or increase the dose of tenapanor based on sP levels and/or GI tolerability. The changes must be made in 10 mg increments to a minimum of 10 mg BID or a maximum of 30 mg BID. The dose of sevelamer carbonate may be adjusted based on the guidance provided in Section 4.1.1 or the sevelamer package insert. Investigators have flexibility to dose sevelamer, TID, BID or QD based on their experience with each patient or as per package insert.

Laboratory efficacy endpoints will be assessed at various times throughout the study; sP will be measured at every visit.

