#### **Sevelamer Arm**

If patients are from the TEN-02-301 sevelamer arm, tenapanor dose will be added based on their baseline sP as described below. Investigators may decrease or increase the tenapanor dose based on sP levels and/or GI tolerability in 10 mg increments to a minimum of 10 mg QD or a maximum of 30 mg BID, not more than once daily. Dosing regimens can be adjusted based on the most recent sP laboratory data (central laboratory data or standard of care local laboratory data).

- sP >2.5 and ≤3.5 mg/dL: add three 10 mg tablets of tenapanor QD and Sevelamer dose can be lowered by one 800 mg tablet TID.
- sP > 3.5 and  $\leq 4.5$  mg/dL: add three 10 mg tablets of tenapanor QD
- sP  $\geq$ 4.5: add three 10 mg tablets of tenapanor BID

If sP > 4.5 mg/dL at next visit

 add three 10 mg tenapanor tablets, if on QD regimen to a maximum of 30 mg tenapanor BID. If on 30 mg tenapanor BID follow sevelamer dose regimen changes described below.

Sevelamer dose can be increased by at least one 800 mg tablet at the largest meal and up to one 800 mg tablet TID; Investigators have flexibility to dose sevelamer BID or QD based on their experience with each patient or as per package insert. If sP <2.5 mg/dL at any visit:

- Sevelamer dose can be lowered by one 800 mg tablet TID; Investigators have flexibility
  to dose sevelamer BID or QD based on their experience with each patient or as per
  package insert.
- If patient is not taking sevelamer then tenapanor dose can be lowered by one 10 mg tablet BID, unless already at tenapanor 10 mg BID, then can dose tenapanor 10 mg QD

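### The protocol's safety tables are grouped by TEN-02-301 arm, which is not the tenapanor-alone versus combination comparison that the secondary safety objective sets

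*Combined protocol and SAP*

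**What the plan says.** Section 3.2, repeated in the Synopsis, lists this secondary objective: "To compare the long-term safety of tenapanor alone and in combination with sevelamer". It is a comparison of regimens.

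The protocol describes the safety analysis twice, with the same grouping each time. The Synopsis says: "All safety measures will be descriptively summarized for the Safety Analysis Set and each TEN-02-301 treatment arm (tenapanor or sevelamer"). Section 9.4.7 says: "These summaries will be provided for the Safety Analysis Set and each TEN-02-301 treatment arm (tenapanor or sevelamer"). Neither splits safety results by regimen received, and neither says which regimen an event belongs to once sevelamer has been started or stopped.

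On who receives what, section 4.1 says that patients from the "TEN-02-301 tenapanor arm will either receive only tenapanor or be given sevelamer in addition to tenapanor based on their sP". Section 4.1.1 lets this change later in that arm: "If sP is still greater than or becomes >4.5 mg/dL at a subsequent visit, sevelamer dose can be increased in a stepwise manner". For the other arm, section 4.1 says: "Patients from the TEN-02-301 sevelamer arm will be given tenapanor in addition to their sevelamer dose". The sevelamer-arm rules in section 4.1.1 also provide for patients who are off sevelamer: "If patient is not taking sevelamer then tenapanor dose can be lowered by one 10 mg tablet BID".

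Section 9.4.3 does plan a monotherapy-versus-combination comparison, but only for serum phosphorus (sP) endpoints. Section 9.1 refers to a separate SAP, which prevails where it differs from the protocol.

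**The concern.** The protocol names a comparison and then specifies tables built on another one. A reader who wants to know whether adding sevelamer changes the safety of tenapanor will have two arm columns and a total. The tenapanor-arm column pools both sides of the question, and the total pools everything.

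The arms also differ in a second way. Tenapanor-arm patients completed TEN-02-301 (section 5.1) and continue at the dose they were receiving at its end (section 6.1.3). Sevelamer-arm patients have tenapanor added at entry. Sections 2.5 and 7.2.7.1 describe looser and more frequent stools as a known effect of tenapanor. A difference between arms in gastrointestinal events could therefore reflect new exposure in one arm and selection for tolerance in the other, and not the combination.

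What is at stake is a stated secondary safety objective, and the risk that an arm difference, or the lack of one, is reported as if it answered that objective.

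**Working it through.** The plan states no figure on this point, and the sample size in section 9.2 has no statistical basis, so there is nothing to reproduce. The check compares the texts and then illustrates the dilution.

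**Does arm identify regimen?**

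| TEN-02-301 arm | Regimen at entry | Possible change later | Tenapanor history at entry |
|---|---|---|---|
| Tenapanor | Tenapanor alone or combination, by sP | Sevelamer may be added, raised or lowered | Completed TEN-02-301, continuing |
| Sevelamer | Combination | Sevelamer may be lowered; patients off sevelamer are foreseen | Tenapanor newly added |

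Sources: sections 4.1, 4.1.1, 5.1 and 6.1.3. Neither arm corresponds to a single regimen throughout.

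**Dilution**

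Inputs, all assumed because the documents give none:
- f1 and f2: shares on tenapanor alone in the tenapanor and sevelamer arms
- m and c: event risk on tenapanor alone and on the combination, with m = 30% and c = 45%, a true difference of 15 points
- risk depends only on regimen

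Risk in the tenapanor arm = f1 × m + (1 - f1) × c

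Risk in the sevelamer arm = f2 × m + (1 - f2) × c

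Arm contrast (sevelamer minus tenapanor) = (f1 - f2) × (c - m)

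Fraction of the true difference recovered, with the contrast in points (fraction × 15) in brackets:

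| f1 | f2 = 0 | f2 = 0.1 | f2 = 0.2 |
|---|---|---|---|
| 0.7 | 70% (10.5) | 60% (9.0) | 50% (7.5) |
| 0.5 | 50% (7.5) | 40% (6.0) | 30% (4.5) |
| 0.3 | 30% (4.5) | 20% (3.0) | 10% (1.5) |

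When f1 = f2, for example both 0.2, the contrast is zero whatever the true difference. The f2 = 0 column is the most favourable case for the arm tables. The fractions do not depend on the choice of 30% and 45%.

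The formula is exact for proportions of patients if each patient stays on one regimen. It is exact for rates per patient-year, with a constant rate on each regimen, if f1 and f2 are shares of exposure time. For the proportion of patients with an event when patients switch, it is only a guide.

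**Prior exposure**

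Let d be the extra risk in the sevelamer arm from newly starting tenapanor. The contrast becomes (f1 - f2) × (c - m) + d. If the regimens do not differ (c = m), the whole contrast is d. At f1 = 0.5 and f2 = 0, dilution removes 15 - 7.5 = 7.5 points, so d = 7.5 points would restore the right total for the wrong reason. The arm tables cannot separate the two terms. The documents give neither the size nor the sign of d.

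**The case against.** The strongest reply is that the separate SAP governs and may well contain regimen tables, which are the kind of detail a SAP adds. This stands as a limit. A reader might infer that the objective has no supporting analysis anywhere, and the documents cannot show that, because no SAP text is among them. The point does not collapse into missing detail, however: section 9.4.7 states a grouping, and that grouping does not match the objective. Sections 9.4.3 and 9.4.4 defer expressly to the SAP for further specification; section 9.4.7 does not.

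Second, it is tempting to treat the sevelamer arm as wholly on the combination, so that dilution depends on the tenapanor arm alone. The sevelamer-arm rules contradict this, since they cover patients not taking sevelamer. Allowing for it makes the dilution worse.

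Third, a reader might infer that new exposure must make the combination look worse. That is plausible for early gastrointestinal events in the sevelamer arm, but it is an assumption. Starting doses also differ between the arms: by baseline sP in the sevelamer arm, and carried over from TEN-02-301 in the tenapanor arm, with a distribution the documents do not give.

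Fourth, regimen follows sP, so a regimen comparison is confounded too. This is correct, and it means that tables by regimen are descriptive. The planned arm tables are also descriptive, so it is no reason to prefer them for this objective.

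Finally, a non-randomised extension could simply reword the objective to match the arm tables. That would remove the inconsistency, but it would give up the question that the study set itself.

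**Conclusion.** The concern holds for the protocol as written, with medium confidence. The stated safety grouping does not answer the secondary safety objective, because TEN-02-301 arm does not identify regimen in either arm.

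If risk depends only on regimen, the arm contrast shows a fraction f1 - f2 of the true difference: 70%, 50% or 30% at f1 = 0.7, 0.5 or 0.3 with f2 = 0, and less if f2 > 0. These shares are assumptions, and the specified summaries do not report them. Differing prior exposure adds a bias of unknown size and direction, so the net error could go either way.

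The change should be made, as a modest correction. Because section 9.4.3 already separates monotherapy from combination for sP, extending that distinction to safety adds no new concept.

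**What to change.** Keep the arm tables and add the following to section 9.4.7, or confirm that the SAP already contains it:

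1. Descriptive tables of treatment-emergent and serious adverse events by regimen at event onset (tenapanor alone; tenapanor plus sevelamer), with rates per patient-year on each regimen. Show them within each TEN-02-301 arm wherever both regimens occur. State a rule for assigning events and exposure time when sevelamer is started or stopped.
2. Sevelamer-arm treatment-emergent events split by time since the first tenapanor dose, for example up to 3 months and after 3 months. The cut is illustrative.
3. A statement that regimen follows sP, so that the comparison is descriptive and not causal.

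The cost is a few extra tables and one attribution rule, with no new visits or procedures. The downside is a contrast that cannot be read causally.

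One condition must be checked first. Sevelamer dose is collected in some form, because its percent change is an efficacy variable (section 7.3), and dispensing dates are logged (section 6.2.2). But a footnote to the Schedule of Events (section 1.3) allows dose changes by telephone between visits, and the protocol does not say that regimen start and stop dates go into the eCRF. The sponsor should confirm that sevelamer start and stop dates are recorded there, including changes made by telephone. Without them, neither regimen at onset nor patient-years per regimen can be derived reliably.
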